### *Sample Size*

Power calculations were based on a two-sided, two-sample t-test to compare the differences in mean change. Effect sizes were selected based on a trial comparing Acceptance and Commitment Therapy with PCT in veterans with mental health diagnoses, using the SDS (Lang et al., 2016), which showed a large effect size for reduction in disability ( $d \approx .60$ ), a change of 1.2 points. Lang et al.'s (2016) follow-up interval was 3 months. These correspond to 3-month changes of 1.2 points assuming a standard deviation for the change of 2.1 points as per Lang and colleagues. These power calculations inflate the variance to account for clustering of scores (sites by therapists), with an  $ICC = .02$ . To partially offset possible losses to follow-up, we will follow the Benjamini-Hochberg testing procedure, which is less conservative than the Bonferroni rule (Benjamini & Hochberg, 1995). Each hypothesis is powered to compare outcome at 3 months. Analyses up to 6-months post-treatment are exploratory. Testing five hypotheses, each with Type I error of  $1\% = 5\%/5$ , then with 93 participants per arm, a two-sample t-test, comparing the difference between the 3-month changes, has 90% power to detect an absolute difference of .50 or larger assuming an effect size of .56. To have 80% power with 93 participants per arm requires an effect size of .50.

Note: In consultation with RR&D, we recalculated the number of participants to power the original trial at .8 (vs. .9) and this resulted in a new target N of 148 (74 per arm).

**COVID-19 Aim:** We used the AD grant's power framework to estimate the N required to test our hypothesis that AD would lead to better functional changes relative to PCT in COVID-19 stressed veterans with PTSD. We used the same parameters for mean change and the SD for change in Sheehan scores from the grant and a revised differential effect size prediction of .8. We reasoned that we would expect a larger differential effect size for this sub-study because AD can not only help veterans whose existing PTSD symptoms and impairments are exacerbated by COVID-19 stressors but also because AD includes change agents that can help reduce distress and impairment associated with the day to day demands and stressors of living in the time of COVID-19 (mindfulness, loving kindness meditation, letter-writing, behavioral assignments). With these parameters, we need 74 veterans (37 per arm) to power the aim (at a power of 0.90; one-tailed).

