### **ANALYSES**

**Inferential analyses.** The longitudinal and clustered nature of the design produces a multilevel or nested data structure (Raudenbush & Bryk, 2002), with a likelihood of between-subject variability in treatment trajectory over time (e.g. random slopes). In this study, veterans and therapists are nested (clustered) within performance sites. The lower level (level-1) data consists of the repeated measures for each individual at each assessment. Level-1 data is nested within upper level (level-2) person-level variables (e.g., study site).

Using the most up to date statistical software such as SAS 9.4 and R/R Studio, we will explore the change trajectory of endpoints over the course of pre-treatment, during-treatment, and post-treatment time intervals. Specifically, we will use the linear mixed model regression framework to assess the differential treatment effects of endpoint symptom burden over time. We will examine observed measurement scores and specify linear mixed models that best fit the time-change trends (e.g. linear, piecewise). We will test for the presence of random variation, such as between-site cluster effects and between-subject random slopes of treatment effect. We will determine the best fit linear mixed effects model as a combination of most appropriate representation of time and empirically-evidenced random and fixed effects.

The linear mixed effects models will incorporate clinically relevant time-invariant and time-varying predictors and will use Maximum Likelihood Estimation to produce estimates that are unbiased in the presence of random missingness and dropout. They will provide an Intent-To-Treat (ITT) analysis that will incorporate all available data. Per-protocol and “completer” subset analyses will be performed under the same paradigm. Additionally, a subset of subjects whom began therapy during the COVID-19 pandemic will be identified and analyzed separately; they comprise subjects which began therapy following December 31st, 2020. The tenability of the “At-Random” missingness assumption will be assessed and a sensitivity analysis of the results will be conducted to determine robustness of the inferences.

**Aim I:** Randomized controlled trial of AD-E, comparing it to PCT:

**Hypotheses 1 and 2:** Veterans in the AD-E arm will have a steeper downward slope in SDS (primary endpoint). Identical calculations will be performed with the B-IPF and DRRI-2 Post-Deployment Social Support measure.

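### The plan compares arms on SDS change or slope without saying how baseline SDS is handled; a common baseline mean or baseline covariate, with a named 3-month contrast, would probably gain precision

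*Combined protocol and SAP*

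**What the plan says.** All references are to the combined protocol and SAP.

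- **Primary comparison (ANALYSES, Aim I).** "Veterans in the AD-E arm will have a steeper downward slope in SDS (primary endpoint". The other continuous outcomes get models of the same structure.
- **Role of baseline (ANALYSES, Inferential analyses).** The authors plan to "explore the change trajectory of endpoints over the course of pre-treatment, during-treatment, and post-treatment time intervals", so the pre-treatment score is one of the modelled outcome points.
- **Form of the model (same section).** "We will determine the best fit linear mixed effects model as a combination of most appropriate representation of time and empirically-evidenced random and fixed effects". No arm main effect is stated or excluded.
- **Covariates (same section).** "The linear mixed effects models will incorporate clinically relevant time-invariant and time-varying predictors". These are not named, and baseline SDS is not listed.
- **Power (Sample Size).** "Power calculations were based on a two-sided, two-sample t-test to compare the differences in mean change", with a difference of 1.2 points, an SD of change of 2.1, 1% two-sided per hypothesis, and 3 months as the powered time point. The target was reduced from 93 to 74 per arm by moving from 90% to 80% power.
- **Randomisation (Random Assignment).** Blocking is on gender and minority status, not on SDS.

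**The concern.** The t-test behind the sample size takes each arm's own observed baseline mean as its reference. A mixed model with arm, time and arm-by-time terms does the same: its arm-by-time term is a contrast of changes. Each spends information on estimating a baseline arm difference whose expected value is known to be zero when the score is taken before randomisation. The sampling noise in that difference then passes into the treatment effect.

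This costs precision on the primary endpoint and on every continuous outcome that shares the model. The trial has little reserve. N was recalculated for 80% power, no dropout rate is given, and the stated sample sizes reproduce only without any inflation for the ICC of .02. Leaving the handling of baseline open also means that the choice would be made after outcome data have been seen, because fixed effects are to be chosen by fit.

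**Working it through.** **Inputs from the Sample Size section.** Difference 1.2; SD of change 2.1; alpha .01 two-sided; 74 per arm (earlier 93).

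**Inputs assumed.** The baseline to 3-month correlation r and the two cross-sectional SDs are not in the documents, and an SD of change of 2.1 does not determine them. I take r = .3, .5 and .7, and a follow-up to baseline SD ratio q of 1.0, 1.2 and 1.4.

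**Step 1. The plan's own figure.** Standardised difference 1.2/2.1 = .571. Standard error (SE) at 74 per arm = 2.1 × √(2/74) = .345. Noncentral-t power is 80.5% at 74 per arm and 90.1% at 93, so the stated 80% and 90% reproduce, with no clustering inflation.

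**Step 2. Variance of the two contrasts.** With baseline SD s0 and follow-up SD s1, per participant:

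- change score: s0² + s1² − 2·r·s0·s1 (= 2.1² here);
- common baseline mean, or baseline as covariate: s1²(1 − r²).

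With s0 = s1 the variance ratio is (1 − r²)/(2(1 − r)) = (1 + r)/2, so the SE ratio is √((1 + r)/2).

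**Step 3. Equal SDs, SD of change held at 2.1.**

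| r | SE ratio | SE cut | Standardised difference (.571/ratio) | Power, 74 per arm | n per arm for 80% |
|---|---|---|---|---|---|
| .3 | .806 | 19.4% | .709 | 95.4% | 49 |
| .5 | .866 | 13.4% | .660 | 91.8% | 56 |
| .7 | .922 | 7.8% | .620 | 87.5% | 63 |

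**Step 4. Follow-up SD larger than baseline SD.** The SDS entry floor of 10 (Inclusionary Criteria) may narrow the baseline spread. The SE ratio is √(q²(1 − r²)/(1 + q² − 2rq)).

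| q | SE cut at r = .3 / .5 / .7 | Power, 74 per arm |
|---|---|---|
| 1.2 | 12.7% / 6.7% / 1.7% | 91% / 87% / 82% |
| 1.4 | 8.3% / 2.9% / 0.0% | 88% / 83% / 80.5% |

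**Step 5. Can the gain be negative?** Subtracting the second variance in Step 2 from the first gives s0² − 2·r·s0·s1 + r²·s1² = (s0 − r·s1)², which is never below zero. At worst the two analyses tie, apart from the negligible cost of estimating one coefficient.

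**Step 6. More visits and dropout.** I used generalised least squares with time as categories at 0, 3, 6 and 9 months. For the first follow-up contrast it gives the same 19.4/13.4/7.8% under compound symmetry and under AR(1). With an assumed 30% monotone dropout the cut is 17.2/11.7/6.7%. Three random-slope examples gave 12.7% to 15.6% with complete data and 11.1% to 13.7% with that dropout.

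**The case against.** **The text does not say that the baselines are free.** A reader might infer that the plan fits an arm main effect at baseline. It does not say so. Selection by fit could drop that term, and the unnamed predictors could include baseline SDS. This stands. Separate baselines are certain only for the t-test used for sample size. For the mixed model they are the usual reading of a text that leaves the matter open.

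**The gain could be close to nothing.** A reader might take an 8% to 19% saving as a property of this trial. It depends on a correlation and on equal SDs that the documents do not give, and Step 4 shows it nearly vanishing in one corner. This stands, so the gain must be stated as conditional.

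**The change is not free for a slope endpoint.** In a straight-line model, removing the arm intercept alters what the slope estimates if change is not linear. For an effect of 1 point reached by 3 months and then flat, the fitted slope difference is .100 per month with free intercepts. With a common one it is .110 to .127 (compound symmetry, r = .7 to .3). Baseline as covariate with only later visits as outcomes is not equivalent either, because an arm-by-time slope would then describe 3 to 9 months and largely miss the 12 weekly sessions. Both objections stand against a slope. Neither applies to an arm contrast at a named visit with time as categories.

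**The planned analysis is valid.** A reader might infer that chance baseline imbalance biases it. Under randomisation, a comparison of change or slope is unbiased over repeated allocation and its type I error is controlled. The issue is efficiency and specification.

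**The COVID-19 subset.** A reader might extend the gain to it. ANALYSES defines that subset by having begun therapy after 31 December 2020. If therapy starts after assignment, randomisation no longer guarantees equal baseline means within it.

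**Conclusion.** The point holds as a recommended improvement, not as an error that invalidates the analysis. The plan tests change or slope in SDS from pre-treatment and never states a baseline adjustment or a common baseline mean.

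For a 3-month contrast at 74 per arm, difference 1.2, SD of change 2.1 and two-sided 1%, power would rise from 80.5% to about 95% (r = .3) or 87.5% (r = .7) if SDs are equal. The corresponding SE reductions are about 19% and 8%. If follow-up SD exceeds baseline SD, the SE reduction is about 13% to 2% at a ratio of 1.2 and 8% to 0% at 1.4. It is not negative for this contrast. The correlation and the SD ratio are assumptions throughout, and no clustering inflation is included. The documents do not support an unconditional figure, a claim that the change costs nothing, or a power gain for the COVID-19 aim.

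**What to change.** In ANALYSES (Inferential analyses and Hypotheses 1 to 6), specify the following for SDS and the other continuous outcomes:

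1. A mixed model with time as categories.
2. Either the pre-randomisation score kept among the outcomes with one mean common to both arms, or post-randomisation visits as outcomes with the pre-randomisation score as covariate. Choose one in advance.
3. The 3-month arm contrast, the time point powered in Sample Size, as the primary effect. State which visit this is: Objectives counts months from the end of treatment, while Follow-Up Assessments counts them from the first session.
4. The baseline score as the one taken before randomisation. Consent and Pre-Eligibility Screening re-administers baseline measures when therapy starts a month or more later, without saying whether this precedes assignment.
5. The common baseline mean in the COVID-19 subset only if that subset is defined by randomisation date rather than by having begun therapy.

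**Cost.** A short paragraph, with no new data and no more participants. The real change is that the primary effect becomes a difference at a visit rather than a fitted straight-line slope. Slopes can stay as secondary descriptions of trajectory.

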#### **B: Mental health change hypotheses:**

- B.4.** Veterans randomized to AD-MIL will have greater reductions in PTSD symptom severity and a smaller percentage of PTSD cases
- B.5.** Veterans randomized to AD-MIL will have greater reductions in depressive symptoms
- B.6.** Veterans randomized to AD-MIL will have greater reductions in shame and guilt
- B.7.** Veterans randomized to AD-MIL will have greater reductions in psychological distress

We will also explore the impact of treatment on anger and aggressive behaviors, suicidal ideation, alcohol abuse, compassion towards self and others, and social connectedness.

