**Hypotheses 3-6:** Veterans in AD-E will have: (3) steeper downward PTSD symptom severity slopes (CAPS-5 and PCL-5) and lower incidence of PTSD cases (tested with Chi-square); (4) steeper slopes in depressive symptoms (PHQ-9); and (5) steeper slopes in shame and guilt (TRSI and TRGI); (6) steeper slopes in overall psychological distress (SOS) Separate models will be tested for each outcome. These models will be structured the same as the model used to test Hypotheses 1 and 2, with the above continuous measure scores designated as the outcome variables in separate analyses.

**Exploratory analyses:** Will AD-E be associated with steeper downward slopes in anger and aggressive behaviors (DAR-5, CTS2), suicidal ideation (DSI-SS), and alcohol abuse (QDS) as compared to PCT? Will AD-E be associated with steeper upward slopes in compassion towards self (SCS), compassion towards others (SBCS), and social connectedness (SoCS) as compared to PCT? The models used to evaluate these questions will be structured the same as the models above. We will be especially circumspect about statistically significant findings for these variables.

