**Clinical significance:** Clinical significance will be calculated by the Jacobson-Truax (1991) method (e.g., Bauer, Lambert, & Neilson, 2004). This method suggests a two-step criterion. First, a reasonable cutoff between the dysfunctional and functional populations is established. Because normative data for veterans on the SDS does not yet exist, Jacobson and Truax's (1991) suggested cutoff A, defined as the point 2 *SDs* beyond the range of the pre-therapy mean (cutoff A =  $M_{clinical} - 2 SD_{clinical}$ ) will be used. Next, a reliable change index (RC) for each participant will be calculated to ensure that changes are not due to an artifact of measurement error. The RC is computed according to the following:  $RC = (x_2 - x_1)/S_{diff}$  where  $x_1$  represents the participant's pre-treatment SDS total score,  $x_2$  represents the participant's post-treatment or follow-up total score, and  $S_{diff}$  is the standard error of difference between the two test scores.  $S_{diff}$  will be calculated from the internal consistency of the measure at each time point. An RC larger than 1.96 reflects real change. Based on the two-step criterion, individuals will be classified as recovered (passed both cutoff A and RC criteria), improved (pass RC criterion but not cutoff A), unchanged (passed neither criteria), or deteriorated (passed RC criterion but symptom scores increased) for each follow-up interval. Chi-square analyses will be used to compare proportions per arm at each follow-up.

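### PTSD caseness and the SDS clinical-significance categories are tested by unadjusted chi-square, with no missing-data rule, no therapist term and, for caseness, no named visit

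*Combined protocol and SAP*

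**What the plan says.** Hypothesis B.4 has two halves. Veterans given AD-MIL are expected to show "greater reductions in PTSD symptom severity and a smaller percentage of PTSD cases". In ANALYSES, Hypotheses 3-6, severity (CAPS-5 and PCL-5) goes into mixed models, and caseness is covered by "lower incidence of PTSD cases (tested with Chi-square". No visit is named. The same paragraph restricts the mixed models to continuous outcomes, "with the above continuous measure scores designated as the outcome variables in separate analyses".

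The Clinical significance paragraph classifies each veteran on the SDS as recovered, improved, unchanged or deteriorated, and then states: "Chi-square analyses will be used to compare proportions per arm at each follow-up".

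The missing-data provisions are in the Inferential analyses paragraphs. The linear mixed models "will use Maximum Likelihood Estimation to produce estimates that are unbiased in the presence of random missingness and dropout", and of those models the plan says "They will provide an Intent-To-Treat (ITT) analysis that will incorporate all available data". It also promises that "a sensitivity analysis of the results will be conducted to determine robustness of the inferences", naming no method and no outcome. On clustering it says: "We will test for the presence of random variation, such as between-site cluster effects and between-subject random slopes of treatment effect".

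Four other sections bear on the point:

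- Sample Size assumes an ICC of .02 and expects some loss to follow-up.
- Treatment Training, Supervision, and Fidelity Monitoring trains each therapist in one arm only.
- Follow-Up Assessments keeps veterans who stop therapy early on the 3-, 6- and 9-month schedule. It gives some late-randomised veterans only the 3-month visit, or only the 3- and 6-month visits.
- Random Assignment blocks on gender and minority status.

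**The concern.** A chi-square test needs a classified outcome for every veteran it counts. Caseness needs a CAPS-5 at the visit, and the reliable change index needs a follow-up SDS. With no imputation described, the natural default is to analyse whoever was assessed. If missing assessments differ by arm and the missing are more often still cases, the arm that loses more veterans looks better. If the rule is settled only after the data are seen, the choice of rule can decide the result.

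The test also treats veterans of the same therapist as independent. Each therapist works in only one arm, so differences between therapists add directly to the variance of the arm comparison and the nominal p-value is too small.

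Finally, it sets aside information the trial collects: baseline severity, the other follow-up visits and, for the SDS categories, their order.

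**Working it through.** **The plan's own figures.** The documents give no case rate, power or sample size for either chi-square comparison, so there is nothing to reproduce there. The stated size is for the SDS t-test. At two-sided alpha .01 and d = .56, n = 2(2.576 + 1.282)²/.56² ≈ 95 per arm for 90% power, against 93 stated. With 74 per arm, power is 0.797, against 80% stated. Both agree, but only without any ICC inflation.

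**1. Therapist clustering.** Inputs from the documents: 74 per arm, 4 sites, ICC .02, therapists nested in arm. The number of therapists is not stated, so k = 1 to 4 per arm per site is an assumption. Veterans per therapist: m = 74/(4k). Design effect: DE = 1 + (m − 1) × .02. Actual type I error of a nominal test: 2 × [1 − Φ(z/√DE)].

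| k | m | DE | nominal 5% | nominal 1% |
|---|---|---|---|---|
| 1 | 18.5 | 1.35 | 9.2% | 2.7% |
| 2 | 9.25 | 1.17 | 6.9% | 1.7% |
| 3 | 6.17 | 1.10 | 6.2% | 1.4% |
| 4 | 4.63 | 1.07 | 5.8% | 1.3% |

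A beta-binomial null simulation (case rate 50%, nominal 5%) gave 10.4%, 8.1% and 7.1% for k = 1, 2 and 3. These exceed the formula because counts are discrete. With no clustering at all, the exact level of the uncorrected test at 74 per arm and 50% cases is already 5.8%. Site clustering shared equally by the arms gave 5.6% at ICC .02 and 4.7% at ICC .10, so site is not the source of inflation.

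**2. Bias from missing assessments.** The documents give no missing rates, so every input here is assumed: a true case rate of 50% in both arms, and 70% or 80% cases among the missing. Observed rate = (p − miss × p_missing)/(1 − miss).

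- 20% vs 30% missing, 70% cases among the missing: (.5 − .14)/.8 = 45.0% vs (.5 − .21)/.7 = 41.4%, a false difference of 3.6 points.
- 15% vs 30% missing, 70%: 46.5% vs 41.4%, or 5.0 points.
- 15% vs 30% missing, 80%: 44.7% vs 37.1%, or 7.6 points.

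For scale, the standard error in the first scenario is √(.450 × .550/59.2 + .414 × .586/51.8) ≈ 9.4 points, so the bias is about 0.4 standard errors. In the third it is about 0.8.

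**3. Effect of the missing-data rule.** Take invented data with 15 of 74 missing in PCT and 22 of 74 missing in AD-MIL.

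- Assessed veterans only: 35/59 vs 21/52 cases, a difference of 18.9 points, p = 0.046.
- Missing counted as a case: (35 + 15)/74 = 50/74 vs (21 + 22)/74 = 43/74, a difference of 9.5 points, p = 0.23.

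**The case against.** The case against has real force, and several stronger readings fail.

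- A reader might infer that the plan breaks an intent-to-treat promise. It does not. That sentence describes the linear mixed models, which are confined to continuous scores. The categorical outcomes simply have no stated equivalent.
- A reader might infer that everyone who drops out of treatment is lost. Follow-Up Assessments keeps early terminators on schedule and offers the CAPS-5 by phone from home. Only missed assessments are lost, together with the later visits that some late-randomised veterans do not have by design.
- A reader might infer that caseness is tested at every visit. Repetition is stated only for the SDS categories. For caseness the visit is left open.
- A reader might infer that the continuous outcomes are protected from clustering. Their models name a site effect and subject slopes, kept if the data support them, and no therapist effect. The therapist gap is therefore not peculiar to chi-square.
- Analysis of assessed veterans only is itself an inference. Strictly, the handling is unspecified, and a general sensitivity analysis is promised.

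It is also fair that leaving out baseline severity costs precision rather than validity in a randomised comparison, that the bias scenarios are assumed and stay below one standard error, and that a model assuming data missing at random does not remove bias from informative missingness.

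What remains is that two planned comparisons lack a missing-data rule and a therapist adjustment, one lacks a visit, and a better-suited analysis needs no new data.

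**Conclusion.** The point holds as an under-specified and avoidably weak analysis of secondary outcomes. The primary SDS slope and the severity half of B.4 do not depend on these tests.

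At the plan's ICC of .02, a nominal 5% chi-square has a type I error of roughly 6% to 9%. That range rests on an assumed 4 down to 1 therapists per arm per site, about equal caseloads, and the stated ICC applying to these outcomes.

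The missing-data figures show what could happen and do not predict it. The false advantage is 3.6 to 7.6 points under the assumed rates, and the unstated rule can move a result across 0.05.

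**What to change.** **Caseness.** Make the inferential analysis a logistic mixed model, or GEE, on all follow-up visits, with arm, visit, arm by visit, baseline CAPS-5 severity, site, gender, minority status and a therapist term. All veterans are cases at entry by eligibility, so baseline severity, not baseline caseness, is the covariate. Report the marginal risk difference at one named visit. Sample Size powers each hypothesis at 3 months. Say from which start that is counted, because hypothesis A.1 counts from the end of treatment and Follow-Up Assessments from the first session.

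**SDS categories.** Use an ordinal version of the same model with baseline SDS. Keep the chi-square tables as description.

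**Missing data.** State the rule in advance. The mixed model assumes data missing at random, and standard GEE needs a stronger assumption unless combined with multiple imputation or weighting. Add a sensitivity analysis that counts missing as a case, or another missing-not-at-random analysis. Treat visits absent by design separately from missed ones.

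**Therapists.** State how many there are, and consider the same term in the continuous models.

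**Cost.** Somewhat more programming and explanation, and no new data. The random effects may have to be simplified at N = 148, GEE would need a small-sample correction with few therapists, and proportional odds is an assumption to check. Fix the order of simplification before unblinding.

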**PTSD Checklist for DSM-5 (PCL-5; Weathers et al., 2013b).** The PCL-5 will also be used to examine PTSD symptom burden. At the pre-eligibility screening, site RAs will ask veterans to write a one-sentence description of their worst and most currently distressing warzone experience on the top of the PTSD Checklist for DSM-5 (PCL-5) page and to rate symptoms referencing this event on the PCL-5. The PCL-5 will also be administered each week during therapy to track progress, capture adverse outcome, and model within-treatment change. The PCL-5 is similar to the PTSD Checklist (PCL) based on the DSM-IV. The PCL-IV has excellent psychometric characteristics (McDonald & Calhoun, 2010). The PCL-5 has 20-items which are scored in the past month on a scale from “0 = not at all” to “4 = extremely.”

Hypothesis B.5.

**Patient Health Questionnaire (PHQ-9).** This widely used and well-validated (Kroenke et al., 2001) measure will be used to measure depression. It has high internal consistency (e.g., Cameron et al., 2008) and correlates strongly with other measures of depression (Kroenke et al., 2001);

Hypothesis B.6.

**Trauma-Related Guilt Inventory (TRGI; Kubany et al., 1996).** The TRGI assesses guilty feelings and attitudes about a specific warzone event. It is scored into three scales (Global Guilt, Distress Scale, and Guilt Cognitions) and 3 subscales (Hindsight-Bias/Responsibility, Wrongdoing, and Lack of Justification).

**Trauma-Related Shame Inventory –Internal Shame Subscale (TRSI; Øktedalen et al., 2014).** The TRSI internal shame subscale is a 12-item self-report instrument designed to assess individuals' negative self-evaluations in the context of their traumatic experiences. The measure has good construct validity (Øktedalen et al., 2014).

Hypothesis B.7.

**The Schwartz Outcome Scale-10 (SOS-10; Blais et al., 1999).** Psychological health and distress will be measured using the SOS-10, a 10-item general mental health outcome measure. The SOS-10 has demonstrated good psychometric properties.

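### The weekly PCL-5 may inherit a random-effects structure chosen on about four SDS visits; the text should settle this and pre-specify a subject slope of time

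*Combined protocol and SAP*

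**What the plan says.** The ANALYSES section (Inferential analyses) proposes linear mixed models. The form of time is picked by fit, linear or piecewise being the examples, and the final model contains "empirically-evidenced random and fixed effects". On the random part it says: "We will test for the presence of random variation, such as between-site cluster effects and between-subject random slopes of treatment effect". No test, threshold or keep-or-drop rule is given. The same section opens by describing the data as nested, "with a likelihood of between-subject variability in treatment trajectory over time (e.g. random slopes").

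Hypotheses 1 and 2 concern the SDS slope, the primary endpoint, with the B-IPF and the social support scale handled identically. For Hypotheses 3-6, which include the CAPS-5 and PCL-5 slopes, each outcome has its own model, but "These models will be structured the same as the model used to test Hypotheses 1 and 2". PTSD caseness is compared by Chi-square and lies outside this rule.

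The schedules differ. The Measures section says: "The PCL-5 will also be administered each week during therapy to track progress, capture adverse outcome, and model within-treatment change". Treatment is 12 weekly sessions. For the SDS, four occasions (baseline, then 3, 6 and 9 months) is my inference from the baseline procedures and Follow-Up Assessments. No SDS schedule is stated, and some late enrollees have only one or two follow-ups.

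**The concern.** A four-occasion outcome and an outcome with about 12 further weekly occasions need not support the same random effects. If the SDS data do not show a subject slope and it is dropped, a PCL-5 model built the same way has only a subject intercept. It then treats about 13 closely spaced scores per veteran as independent around that veteran's level. Where veterans differ in their rate of change, the standard error of the arm-by-time term is too small. The PCL-5 slope serves hypothesis B.4, which is not exploratory, so a PTSD-symptom benefit could be declared more often than the stated error level allows.

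A smaller wording problem sits beside this. The term to be tested is called "between-subject random slopes of treatment effect". Each veteran receives one arm, so a veteran-specific treatment effect cannot be separated from other variation between veterans. The usable term is a random slope of time.

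**Working it through.** **The plan's own figure.** The documents give no error rate for the slope tests. The design figure used below is 74 per arm (Sample Size). At two-sided 1% and 80% power, n = 2(2.576 + 0.842)²/d². With d = 0.56 this is 2 × 11.68/0.3136 = 74.5, so 75. With d = 1.2/2.1 = 0.571 it is 72. The stated 74 is reproduced to within two, before any inflation for clustering.

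**Step 1: false rejection if the slope is omitted.** Assumptions not in the documents: PCL-5 at weeks 0-12, linear time, complete data, SD of true individual 12-week change D = 5-15 points, residual SD s = 5-8 points. Then m = 13, Sxx = 182 and the slope SD is τ = D/12.
- True variance of a veteran's fitted slope: τ² + s²/Sxx.
- Variance assumed by the intercept-only model: (s² + τ²Sxx/(m−1))/Sxx.
- Ratio: R = (1 + L)/(1 + L/12), with L = τ²Sxx/s².
- False rejection: 2(1 − Φ(z/√R)), with z = 1.96 or 2.576.

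| D, s | L | R | nominal 5% | nominal 1% |
|---|---|---|---|---|
| 5, 8 | 0.49 | 1.43 | 10.2% | 3.2% |
| 10, 6 | 3.51 | 3.49 | 29.4% | 16.8% |
| 15, 5 | 11.38 | 6.35 | 43.7% | 30.7% |

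Simulation with 148 subjects agrees: 8.9% to 43.6% at nominal 5% for D/s from 0.5 to 3. With a subject slope allowed for, it gives about 3.5-6.3%.

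**Step 2: would the SDS screen drop the slope?** Assume 148 complete cases, visits at 0, 3, 6 and 9 months (Sxx = 45), and a 5% F test of between-veteran slope variance on 146 and 296 df (critical value 1.26). Let k = D/s be the same for both measures, and take 12 weeks as 3 months.
- *Change continues linearly to month 9.* The expected mean-square ratio is 1 + 45(k/3)² = 1 + 5k². At k = 0.5 it is 2.25 and the slope is kept more than 99.9% of the time. At k = 0.25 it is kept about 61% of the time, but the PCL-5 error when it is dropped is then only 5.8%. Overall: 0.39 × 5.8 + 0.61 × 5 = 5.3%. If the three follow-ups are added to a single linear PCL-5 slope, overall error is still at most about 7% on the grid examined.
- *Change occurs in therapy, then plateaus, while time is modelled as linear.* The individual pattern over the four visits is 0, 1, 1, 1. Its linear component contributes 0.45k² to the slope mean square. The remaining 0.30k², over 2 df per veteran, contributes 0.15k² to the residual. The ratio is (1 + 0.45k²)/(1 + 0.15k²).

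For the plateau case, overall error = P(drop) × error when dropped + P(keep) × 5%:

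| k | ratio | kept | error if dropped | overall at 5% |
|---|---|---|---|---|
| 0.5 | 1.07 | 13% | 8.3% | 7.9% |
| 0.75 | 1.16 | 27% | 12.3% | 10.3% |
| 1.0 | 1.26 | 50% | 17.1% | 11.1% |
| 1.25 | 1.38 | 73% | 22.0% | 9.6% |
| 10/6 | 1.59 | 94% | 29.4% | 6.5% |

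At nominal 1%, k = 1 gives 0.5 × 7.2 + 0.5 × 1 = 4.1%. The F approximation ignores that the lack of fit is shared within a veteran. Direct simulation gives similar figures, and the range across these checks for k from 0.5 to 1.25 is about 8-12%.

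**The case against.** The strongest reply is that the rule is not as rigid as it looks. The selection procedure is written for endpoints and models in the plural and covers the during-treatment interval, which suits a weekly outcome. Each outcome also has its own model. Having the same structure can mean the same framework and selection procedure, applied afresh. That reading is available, and nothing says that variance terms are screened on the SDS and then frozen. What remains is an ambiguity: two competent analysts could report different PCL-5 standard errors from this text.

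Secondly, the plan expects random slopes, and a sample of 148 would usually detect them on the SDS if they vary there as they do on the PCL-5. The SDS here rates impairment due to PTSD symptoms, so a large gap between the two is not the natural expectation. This stands for linear change to month 9. It is weaker if change stops when therapy ends, because a straight line over four visits then captures little of it. A piecewise SDS form would do better, but that choice is left to the data.

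Thirdly, B.4 does not rest on the PCL-5 alone: the CAPS-5 slope and caseness also bear on it. That limits the consequence and stands.

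A reader might also infer that the plan intends a term that cannot be estimated. The opening reference to trajectories over time indicates that a slope of time is meant, so this is loose wording to be reconciled.

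**Conclusion.** The point holds as a specification gap with a conditional consequence. If the subject slope is dropped, PCL-5 false rejection is about 10-44% at nominal 5% and 3-31% at the plan's 1% per hypothesis, under variances that the documents do not give. Allowing for the screen, and with equal relative slope variation in both measures, overall error is near nominal under linear change to month 9. It is about 8-12% at nominal 5% under a plateau, for SD ratios of roughly 0.5 to 1.25, and falls back towards nominal as the ratio rises.

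A reader might take 10-44% as the trial's expected false-positive rate. The documents do not support that: its upper part needs strong PCL-5 slope variation together with SDS variation that the screen misses. Nor do they support saying that every other outcome must reuse the SDS structure, since PTSD caseness and the clinical-significance classes use Chi-square. All figures assume complete, balanced data, no site or therapist effects and a 5% screen, which the plan does not specify. Four SDS visits is inferred and does not apply to all late enrollees.

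**What to change.** In the Hypotheses 3-6 paragraph of ANALYSES, replace the same-structure sentence with a statement that the time form is chosen separately for each continuous outcome. Pre-specify a subject random intercept and a random slope of time, at least for the weekly PCL-5, whatever the SDS screen shows. In the Inferential analyses paragraph, change "between-subject random slopes of treatment effect" to random slopes of time, to match that section's opening description. Separate in-therapy and post-therapy segments or serially correlated residuals for the PCL-5 are reasonable options, but the point does not depend on them.

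The cost is a few sentences, a few extra variance parameters, and slightly wider intervals where slopes do not vary. No new data or participants are needed.
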